5.5 CRITERIA FOR TEMPORARILY DELAYING ADMINISTRATION OF STUDY INTERVENTION

Not applicable.

6 STUDY INTERVENTION AND CONCOMITANT THERAPY

Study intervention is defined as any investigational intervention(s), marketed product(s), or placebo intended to be administered to a study patient according to the study protocol.

6.1 STUDY INTERVENTION (S) ADMINISTERED

Product Name: PRN473 (SAR444727)

Table 4 - Study intervention

	PRN473	Placebo
Drug Name	PRN473 Gel, 5%	PRN473 Gel, Placebo
Type	Drug	Placebo
Dose Formulation	White to off-white gel suspension containing PRN473, inactive ingredients (propylene glycol, glycerin, polysorbate 80, medium chain triglycerides, Carbopol 980, preservatives [methylparaben and propylparaben], and water). The gel suspension is adjusted to pH 5.	White to off-white gel suspension containing the same inactive ingredients, except that titanium dioxide used to match the color of PRN473 active ingredient.
Unit Dose Strength(s)	5% (w/w)	0%
Dosage Level(s)	5% (w/w) gel at 2.5 mg gel/cm ² over 100 cm ² BID (Blinded Period) or up to 14% BSA BID (Open-Label Period)	Matching placebo at 2.5 mg gel/cm ² over 100 cm ² BID (Blinded Period)
Route of Administration	Topical	Topical
Use	Experimental	Experimental
IMP or NIMP	IMP	IMP
Sourcing	Provided centrally by the Sponsor	Provided centrally by the Sponsor
Packaging and Labeling	PRN473 Gel products are filled into aluminum tubes (approximately 30 g in each aluminum tube).	Placebo Gel products are filled into aluminum tubes (approximately 30 g in each aluminum tube).
Former Name(s) or Alias(es)	SAR444727	not applicable

Abbreviations: API = active pharmaceutical ingredient; IMP = investigational medicinal product; NIMP = non-investigational medicinal product.

6.2 PREPARATION/HANDLING/STORAGE/ACCOUNTABILITY

The Sponsor will supply the study intervention to the study site. The study intervention provided for this study was manufactured under Current Good Manufacturing Practices (CGMP) and will be suitable for human use. The Sponsor is responsible for the preparation and labelling and providing details of batch numbers, safety, and stability data. The study intervention will be labelled in accordance with local regulatory requirements and will be shipped at a temperature of 2-8°C.

The Investigator or designee must confirm appropriate temperature conditions have been maintained during transit for all study intervention received and any discrepancies are reported and resolved before use of the study intervention. The recommended storage condition is 2-8°C (Investigator's Brochure).

Only patients enrolled in the study may receive study intervention, and only authorized study staff (eg, site staff, trained medical professional, home health vendor, external clinic staff, etc) may supply or administer study intervention during the Blinded Period. At the study site, all study intervention must be stored in a secure, environmentally controlled, and monitored (manual or automated) area in accordance with the labeled storage conditions with access limited to the Investigator and authorized site staff.

The Investigator, institution, or the head of the medical institution (where applicable) is responsible for study intervention accountability, reconciliation, and record maintenance (ie, receipt, reconciliation, and final disposition records). When the study is completed, the Investigator will return or destroy any used and unused trial medication (eg, empty, partially used, and unused containers) to the Sponsor as requested.

The Investigator or designee is responsible for the education of site staff as to the correct administration of the study intervention.

When operationally feasible and if treating physician determines that it is appropriate and safe, administration of IMP may occur at study patient's home or at an external clinic by a trained medical professional. These approaches will only be implemented if allowed by local regulations, and agreed by the treating physician, while ensuring blinding measures are maintained.

Patients are required to apply an emollient (except urea-containing or medicated emollients that are regulated as medical device) daily from Day -7 to Day 1. Beginning on Day 1, emollient is to be applied only on untreated areas (eg, may not be used on the 2 target lesions during Days 1-14, and may not be used on any parts of the body being treated with PRN473 Gel, 5% during Days 15-42).

PRN473 Gel, 5% or matching placebo will be removed from storage at 2-8°C and held at room temperature for at least 30 minutes prior to administration. Site staff or trained medical professional will apply PRN473 Gel, 5% or matching placebo with nitrile gloves to the 2 target lesions per the randomization assignment, as follows:

- Approximately 2.5 mg gel/cm² to each 100 cm² target lesion on Days 1-14. If the target lesion is less than 100 cm², the application area should include surrounding nonlesional skin; if the target lesion is larger than 100 cm², only 100 cm² of the lesion should be marked and treated.
- On Days 15-42 (open-label period), patients are instructed to apply PRN473 Gel, 5% BID to all AD-affected areas in a thin layer, excluding the scalp, palms, soles, and genitals.

Under no circumstances will the Investigator supply study intervention to a third party (except for direct to patient [DTP] shipment or direct to designated clinic for home health care option if patient is not able to be dosed at home, for which a courier company has been approved by the

Sponsor), allow the study intervention to be used other than as directed by this clinical trial protocol, or dispose of study intervention in any other manner.

Intervention units are returned by the patient at each visit. In case of DTP process, the intervention units can be returned by the carrier (if defined in the contract).

Further details will be outlined in the Pharmacy Manual.

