4.3 JUSTIFICATION FOR DOSE

Product Name: PRN473 (SAR444727)

The dose of PRN473 selected for topical administration during the Blinded Period on Days 1-14 in PRN473-0005 (ACT17131) is PRN473 Gel, 5% or matching placebo at approximately 2.5 mg/cm² over a 100 cm² area encompassing each target lesion BID (approximately 12 hours apart). During the Open-Label Period on Days 15-42, PRN473 Gel, 5% at 2.5 mg/cm² will be applied BID to all AD-affected areas excluding the scalp, palms, soles, and genitals over a body surface area of up to 14%. This dose is in the range of those associated with biological activity based on preclinical disease models and is therefore considered appropriate to evaluate in this initial assessment of PRN473 Gel efficacy in patients with AD.

The proposed dosing regimens are supported by clinical safety data from the PRN473-0002 study. The total daily dose during the Blinded Period of the study (25 mg PRN473 active pharmaceutical ingredient [API] per day) is approximately 7-fold lower than the daily dose applied in the multiple dose arm of PRN473-0002 (175 mg PRN473 API per day). This dose was safe and well-tolerated and there were no serious adverse events (SAEs) or AEs that led to discontinuation.

In the Open-Label Period, the dosing regimen of PRN473 5% (w/w) gel at 2.5 mg/cm² gel over 14% BSA BID will provide a daily PRN473 (API) dose of 665 mg to a patient with a total body surface area of 1.9 m². This is less than the dose of 700 mg PRN473 (API), which was the highest dose administered in the PRN473-0002 single ascending dose/multiple dose study in healthy participants. This dose was safe and well-tolerated and there were no SAEs or AEs that led to discontinuation.

Patients will measure the dose by the fingertip unit method and the expected dose variability when the compound is topically self-applied by this method may be up to two-fold excess of compound which is reasonably below the safety margin.

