6.5 DOSE MODIFICATION

No dose modifications will be permitted.

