6.7.4 Rescue medicine

Rescue topical medications use will be at the discretion of the Investigator after discussion with the Medical Monitor if the patient is flaring above 14% treatable BSA (excluding scalp, palms, soles and genitalia) during the last two weeks of the Open Label Period. Investigators should make every attempt to conduct efficacy and safety assessments (eg, disease severity scores, safety labs) immediately before administering any rescue treatment. An unscheduled visit may be used for this, if necessary. Patients who receive rescue treatment will be asked to continue with study treatment and procedures.

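### The open-label instructions set no limit on treated area, while Table 4 and Section 4.3 put it at up to 14% BSA, and no passage ties the BSA measured on Days 15 and 29 to that figure

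*Protocol*

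**What the plan says.** **Where an area figure is given.** Protocol Section 4.3 describes open-label application "over a body surface area of up to 14"%. The dosage row of Table 4 (Section 6.1) gives "up to 14% BSA BID (Open-Label Period"). Section 4.3 works this out as 665 mg of active ingredient (API) per day for a patient of 1.9 m² and notes that it is below 700 mg, the highest dose given in Study PRN473-0002. Inclusion criterion 6 sets 14.0% as the upper limit at entry.

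**Where none is given.** Section 6.2 states that "patients are instructed to apply PRN473 Gel, 5% BID to all AD-affected areas in a thin layer, excluding the scalp, palms, soles, and genitals". Sections 1.1, 1.2, 4.1 and 6.3 carry the same instruction without a limit, as does the design summary in SAP Section 1.1. Protocol Sections 1.1, 1.2 and 4.1 add that patients keep treating the areas assigned to them throughout the period.

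**When BSA is measured.** The Schedule of Activities has treatable BSA at Screening and on Days 15, 29 and 43, but not on Day 1.

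**What happens above 14%.** Section 6.7.4 allows rescue topicals "if the patient is flaring above 14% treatable BSA (excluding scalp, palms, soles and genitalia) during the last two weeks of the Open Label Period", and adds: "Patients who receive rescue treatment will be asked to continue with study treatment and procedures". Section 7.1.1 requires permanent discontinuation for a change in meeting the eligibility criteria that is clinically relevant and affects safety. It does not mention BSA.

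**The concern.** Open-label dose is set per cm², so treated area determines the total daily dose. Section 4.3 supports that dose only up to 14% BSA, yet the passages a site would follow do not carry the figure. If a patient's treatable BSA is above 14% on Day 15, Section 6.2 points to the whole affected area and Table 4 to no more than 14%. The value that reveals the problem is recorded at the visit where open-label dosing starts, but no passage says how it bears on the area treated.

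The sponsor had this situation in view. The amendment history records that the text of 6.7.4 answered a regulator's comment about patients who flare above 14% in the open-label period. The current text covers only the second half of that period.

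If the situation arose, two sites could handle the same patient differently. One patient would receive more than the amount 4.3 discusses. The other would have untreated lesions counted in whole-body EASI, vIGA-AD and BSA on Days 29 and 43. The planned outputs would not clearly separate them: SAP Section 3.6.1 measures compliance in administrations or days, not area. Section 8.3.7 defines overdose as more than twice the intended dose, which itself depends on the passage followed.

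**Working it through.** **Inputs.** Application rate 2.5 mg gel/cm², strength 5% w/w, twice daily (Table 4); body surface 1.9 m² = 19,000 cm², and comparison dose 700 mg API (Section 4.3).

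**Step 1: reproduce the plan's figures.** Daily API = body surface (cm²) × fraction treated × 2.5 × 0.05 × 2.

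- Open label at 14%: 19,000 × 0.14 × 2.5 × 0.05 × 2 = 665 mg/day, as stated.
- Blinded Period: 100 × 2.5 × 0.05 × 2 = 25 mg/day, and 175/25 = 7-fold, as stated.

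**Step 2: margin in the 4.3 comparison.** 700 − 665 = 35 mg, or 5% of 700. The fraction at which 700 mg is reached is 700 / (19,000 × 2.5 × 0.05 × 2) = 700/4,750 = 14.74% BSA, which is 0.74 percentage points above the stated area.

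**Step 3: if all affected skin is treated.** The BSA values above 14% are assumptions, because the documents give no distribution.

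| Treatable BSA | API per day at 1.9 m² |
|---|---|
| 14% | 665 mg |
| 15% | 712.5 mg |
| 18% | 855 mg |
| 20% | 950 mg |

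Body size matters too. The BSA at which 700 mg is reached is 17.5% at 1.6 m², 14.0% at 2.0 m² and 12.73% at 2.2 m² (body sizes other than 1.9 m² are also assumptions).

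**Step 4: age of the entry value.** Screening may be as early as Day -35. With no Day 0, Day -35 to Day 1 is 35 days and Day 1 to Day 15 is 14 days, so the last scheduled BSA before the switch can be 49 days old.

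**Step 5: which days are covered.** Days 15-42 are 28 days. The last two weeks are Days 29-42, so 6.7.4 covers 14 of the 28. On Days 15-28 the nearest provision is the eligibility clause in 7.1.1, which needs a judgement of clinical relevance and effect on safety.

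**Step 6: effect on the overdose definition.** At 18% BSA and 1.9 m², twice the intended dose is 2 × 665 = 1,330 mg/day if the area stops at 14%, and 2 × 855 = 1,710 mg/day if all affected skin is treated.

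**The case against.** The other side has a good case on several points.

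- **The two phrases can coexist.** Section 4.3 puts them in one sentence, and every enrolled patient meets the 14% limit at entry. A reader might infer that sites must always break one passage or the other. They need not: the conflict arises only for a patient who goes above 14% after entry. That case is not excluded, however.
- **Days 15-28 are not without any rule.** Section 7.1.1 could be invoked, and Section 8 sends immediate safety concerns to the Medical Monitor. This stands, but neither passage names BSA.
- **Eligibility is rechecked.** The Schedule of Activities has a predose eligibility check on Day 1. This stands, though no BSA measurement is scheduled that day.
- **Drift above 14% is not shown.** Inclusion criterion 4 requires stable disease before screening, and exclusion criterion 5 removes unstable disease. Against that, topical treatments are washed out for 4 weeks before Baseline and only two 100 cm² areas are treated in the Blinded Period. The documents settle it neither way.
- **Section 6.5 does not speak to area.** It says "No dose modifications will be permitted". Reading that as a bar on limiting the treated area goes beyond its words.
- **The protocol accepts some excess.** Section 4.3 regards up to two-fold over-application as below the safety margin, 2 × 665 = 1,330 mg/day at 14% and 1.9 m², and Section 4.3 also reports negligible systemic exposure in Study PRN473-0002. So a value above 700 mg cannot be read as demonstrated harm. The two-fold allowance concerns fingertip-unit measurement, though, not a larger area.
- **Continued gel after rescue is a stated choice**, not an error. What stays unclear is the area then treated, because the note to Table 5 allows only study intervention on treated areas.
- **The SAP already summarises BSA.** Its descriptive statistics include the range at each time point, so a maximum above 14% would show. They would not show how many patients exceeded it or link them to safety and PK, and they are planned on the efficacy population.

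**Conclusion.** The inconsistency is in the current text and should be resolved; its severity is moderate. Table 4 and 4.3 give an open-label area of up to 14% BSA, and the 665 against 700 mg argument depends on it. The operative instructions omit it, and the BSA measured on Days 15 and 29 is not tied to it. At 1.9 m², following 6.2 as written passes the 700 mg comparison above 14.74% BSA.

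A reader might go further and conclude that patients will be overexposed, or that the open-label results will mix two regimens. The documents do not support that. They do not say how many of the up to 40 patients would exceed 14%, and the number may be zero. The mg figures above 665 rest on assumed BSA values and on the nominal 2.5 mg/cm². Open-label efficacy is exploratory and descriptive. The point carries weight because safety is the primary objective and PK the secondary one, and both need a clear definition of the area treated.

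**What to change.** **Protocol.** The sponsor should reconcile Sections 1.1, 1.2, 4.1, 6.2, 6.3, 6.7.4 and 7.1.1 with Table 4 and Section 4.3, so that one consistent statement on treated area applies across Days 15-42. It should be clear how the BSA already measured on Days 15 and 29 bears on that statement, how the sentence on assigned areas relates to it, and what area is meant once rescue has been given. The content of the rule is for the sponsor; none is proposed here.

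**SAP.** Add a count of patients with treatable BSA above 14% at Days 15, 29 and 43, preferably on the safety population, and flag these patients in the open-label safety, PK and EASI outputs.

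**Cost.** Protocol wording, one SAP table and a flag. No new visit or measurement is needed.

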6.3 MEASURES TO MINIMIZE BIAS: RANDOMIZATION AND BLINDING

PRN473 Gel, 5% or placebo will be randomized in a blinded fashion to be administered in each patient to 2 separate target lesions (one lesion with PRN473 Gel, 5%, the other with matching placebo) during the Blinded Period (Days 1-14). During the Open-Label Period (Days 15-42), PRN473 will be administered to all AD-affected areas in a thin layer, excluding the scalp, palms, soles, and genitals.

To minimize bias, all safety and efficacy measurements will be performed by a study staff member who is not involved in the study intervention application during the Blinded Period. If the investigational products are applied at the patient's home or at an external clinic, the local tolerability assessment will be performed by another trained medical professional, different than the person administering the study intervention.

Allocation of lesions on patients to treatment group will proceed through the use of an interactive web response system (IWRS) that is accessible 24 hours a day, 365 days a year. A randomized treatment kit number list will be generated centrally by Sanofi for the study interventions. The study interventions (PRN473 Gel, 5% or matching placebo) will be packaged in accordance with the list. All patients will be centrally assigned to randomized study intervention using an interactive response technology (IRT). Before the study is initiated, the telephone number and call-in directions for the IVRS and/or the log in information and directions for the IWRS will be provided to each site. During the Blinded Period of the study, the treatment each patient receives will not be disclosed to the Investigator, trial center personnel, patients, or the Sponsor's representatives on the clinical study team. Further details for blinding and dispensing of blinded treatment are provided in the Pharmacy Manual.

Access to the randomization code will be limited; all Sponsor personnel (and representatives), and site personnel who are directly involved in the conduct of the trial will be blinded to randomization codes.

The pharmacist or designee will be required to enter or select information that will include, but not be limited to; the user ID, and password, patient number, patient year of birth, as well as other information (as allowed locally). The pharmacist or designee will then be provided with a patient randomization number and treatment assignment. Once patient numbers and randomization numbers have been assigned, they cannot be reassigned. Specific instructions will be provided in the IWRS trial reference guide.

Study intervention will be dispensed at the study visits summarized in the Schedule of Activities. Returned study intervention should not be re-dispensed to the patients.

Sponsor safety staff may unblind the intervention assignment for any patient with an SAE. If the SAE requires that an expedited regulatory report be sent to one or more regulatory agencies, a copy of the report, identifying the patient's intervention assignment, may be sent to Investigators in accordance with local regulations and/or Sponsor policy.

The IRT will be programmed with blind-breaking instructions. In case of an emergency, the Investigator has the sole responsibility for determining if unblinding of a patient's intervention assignment is warranted (eg, in case of available antidote). Patient safety must always be the first consideration in making such a determination. If the Investigator decides that unblinding is warranted, the Investigator should make every effort to contact the Sponsor prior to unblinding a patient's intervention assignment unless this could delay emergency treatment of the patient. If a patient's intervention assignment is unblinded, the Sponsor must be notified within 24 hours after breaking the blind. The date and reason that the blind was broken must be recorded in the source documentation and case report form, as applicable.

- In case of an interim analysis, the Sponsor team that will analyze the data would be composed of a Medical Monitor, a biostatistician, a programmer, and a safety designee. Only the biostatistician and the programmer will have the access to unblinded individual data at the time of the analysis, which will not be provided to other Sponsor team members reviewing the data. They will keep the randomization schedule in a locked area, which is not accessible to the Sponsor's clinical team and will not disclose the randomization or the individual unblinded data before the official opening of the randomization (see Section 9.5).
- The bioanalyst and the pharmacokineticist responsible for the sample analysis and PK evaluation will analyze data under blinded conditions and they will not have access to the randomization schedule.

The Sponsor's clinical study team, Investigator, Medical Monitor, study personnel, and patients are not to make any effort during the Blinded Period to determine which lesions are being treated with PRN473 Gel, 5%, and which are treated with matching placebo.

Only in the case of an emergency, when knowledge of the lesion treatment assignment is essential for the clinical management or welfare of a specific patient, the Investigator may unblind a patient's lesion treatment assignment. However, prior to any unblinding, the Investigator is strongly advised to discuss options with the Medical Monitor, Sponsor, or appropriate study personnel. The Investigator will record in source documentation, the date and reason for revealing the blinded lesion treatment assignment for that patient and the names and roles of personnel unblinded.

As soon as possible, and without revealing the patient's lesion treatment assignment (unless important to the safety of patients remaining in the study), the Investigator must notify the Sponsor if the blind is broken for any reason and the Investigator was unable to contact the Sponsor prior to unblinding.

If the Investigator considers an AE to be of such severity as to require immediate specific knowledge of the identity and dose of the relevant product, the Investigator may break the study code for that patient.

6.4 STUDY INTERVENTION COMPLIANCE

Study intervention will be administered under site staff or trained medical professional supervision during the Blinded Period. The date and time of each dose administered at the study site, at patient's home, or at external clinic will be recorded. The dose of study intervention and patient identification will be confirmed at the time of dosing by site staff or trained medical professional other than the person administering the study intervention. Documentation will include the lesion identification for the patient's 2 target lesions.

During the Open-Label Period, patients will complete a daily diary to record PRN473 administered.

